### Statistic and power calculation

The primary outcome of the project is fat percentage, and among the most important secondary outcomes are aerobic fitness, health-knowledge and well-being. The power calculation is based on the result of the pilot project (Ørntoft et al. 2016). The power calculation is measured with t-test. Some variables are expressed in table below and are based on the development on variables from the pilot study and a study with children from the same age group as on the DCSH (Bendiksen et al. 2014). The calculations are based on a power of 0.80 and p-value of 0.05.

Calculation of number of participants (N) in relation to the evaluation on the DCSH standard program and the assessment of activity and health-program (HIHE).

Power calculation	Intervention group (HIHE)	Standard group	IG vs SG	Delta IG SG Sample size
Fat percentage, intervention period	-9.6 (4.2)	-8.9 (3.7)	-0.6 (2.3)	232
Fat percentage, follow- up period	5.0 (13.4)	8.4 (12.9)	-3.3 (11.2)	182
Aerobic fitness	148 (63)	-106 (83)	254 (85)	4
Health-knowledge	11.9 (23.5)	2.6 (23.7)	9.4 (23.5)	100
Muscle mass	0.6 (0.7)	0.5 (0.9)	0.6 (0.8)	29

Number of participants, 1:1 randomisation	Number of participants with 75% at post-tests
464	580
364	455
8	10
200	250
58	73

The calculations are based upon a randomisation of 1:1, 50% of the participants participate in the standard program. Based on the power calculation, the total number of participants is estimated to be approx. 600 children. This is under the consideration of a completion rate of 75%.

All outcomes will be analyzed by means of linear mixed models including two-way interaction between intervention (standard and intervention) and time (before and after) as fixed effect and child and site as random effects (to account for differences between children and between sites, respectively). Adjustment for age, sex, and possibly other covariates/confounders will also be included as fixed effects in the models.

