## Method

### Design

Approximately 600 boys and girls in the age 7-14 years are recruited from two DCSH. The design is a cross-over design at DCSH level over a two-year period with two intervention groups: A standard group (with the standard program (SG)) and a standard + HIHE (SG+). In SG+ the children will, in addition to the standard program, play recreational football 2x45 min. a week. In SG the children will perform the planned activities according to the schedule. The training in SG+ will be performed indoor or outdoor on grass (depending on the facilities on the specific DCSH) with different football exercises (dribbling, ball control, passes etc.) and small-sided games with high intensity (3v3 to 5v5) on two goals. All training sessions take place on the DCSH or in the immediate vicinity of the DCSH. Every week, a specific football skill is connected with a health message. E.g., the skill of passing the ball to each other is related to respect of each other and avoid bullying.

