### **Recruitment of participants**

The participants are recruited from two DCSH. In the project's cooperation agreement, it is specified that two of the DCSH change practice for one year. In this manner, all the children at the two DCSH are participating in the HIHE intervention, regardless of their participation in tests. To investigate the standard program, all tests will be carried out at both of the DCSH for one year. After the first year the two participating DCSH change intervention group. Alongside the general information about the stay at the DCSH, written information about the study will be provided and subsequently an oral information meeting / parent meeting cf. the description below.

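### Age and sex enter the mixed model without time interactions, so the HIHE effect (intervention × time) is not adjusted for them

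*Combined protocol and SAP*

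**What the plan says.** The section *Statistic and power calculation* of the combined protocol and SAP gives one model for all outcomes: a linear mixed model "including two-way interaction between intervention (standard and intervention) and time (before and after) as fixed effect and child and site as random effects". The random effects are there "to account for differences between children and between sites, respectively". On covariates it says: "Adjustment for age, sex, and possibly other covariates/confounders will also be included as fixed effects in the models". Intervention × time is the only interaction named in the document.

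The allocation is described in more than one way:

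- *Statistic and power calculation*: "The calculations are based upon a randomisation of 1:1, 50% of the participants participate in the standard program".
- *Design*: "The design is a cross-over design at DCSH level over a two-year period with two intervention groups".
- *Recruitment of participants*: under the cooperation agreement "it is specified that two of the DCSH change practice for one year", and later "After the first year the two participating DCSH change intervention group".

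The section on participants and eligibility adds that a house holds 24 to 48 children, aged 7 to 14, who are admitted continuously.

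**The concern.** The HIHE effect is a difference in change. A covariate that is fixed over the stay can confound it only if the arms differ on that covariate and the covariate is related to change. Removing that confounding takes a covariate × time term. A main effect adjusts the level of the outcome, and the before/after contrast has already removed the level.

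The plan refers to confounders, so control of confounding is intended. As written, a report could call the HIHE effect adjusted for age and sex when, with complete pairs, it is the unadjusted number. Under individual 1:1 randomisation this would matter little. Here the arms are built from house-years, so a shift in the age or sex mix of admissions between them goes straight into the estimate.

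**Working it through.** **1. The plan's own figure.** Inputs from the power table (fat percentage, intervention period): difference 0.6, SD 2.3, power 0.80, two-sided 5% (two-sidedness assumed). The normal approximation is n = 2 × (1.96 + 0.8416)² × 2.3² / 0.6² = 230.7, so 231 per arm. The exact t-test gives 232 (power 0.801), which is the plan's number. The same row gives arm SDs of 4.2 and 3.7, pooled √((4.2² + 3.7²)/2) = 3.96, used below as a second SD. The table does not state its units.

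**2. Algebra.** For child *i*, arm A and time t (0 before, 1 after), the model on its ordinary reading is

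y = b0 + b1·A + b2·t + b3·A·t + g1·age + g2·sex + child + site + error.

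Subtracting before from after leaves b2 + b3·A + error. Age, sex, child and site have gone. With complete pairs, b3 is estimated by the difference in mean change, whatever g1 and g2 are. If change truly depends on age and sex with slopes d1 and d2, the estimate is centred on

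b3 + d1 × (arm gap in mean age) + d2 × (arm gap in sex proportion).

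**3. Simulation, complete pairs.** Set-up: 600 children, two houses × two years in opposite arms, true effect −0.6, SD of change 2.3, child SD 5, age SD 1.7, age slope of level 0.5 (these last three assumed), 400 replicates.

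| Age gap × slope of change (assumed) | Unadjusted | Age, sex main effects | Age, sex × time |
|---|---|---|---|
| 0.5 y × 0.1 | −0.546 | −0.546 | −0.595 |
| 0.5 y × 0.3 | −0.450 | −0.450 | −0.602 |
| 1 y × 0.3 | −0.297 | −0.297 | −0.595 |

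The first two columns differed by 0.0000 in all 12 scenarios run. A separate REML fit (1-year gap, 10-point sex gap, 150 replicates) gave −0.87, −0.87 and −0.62.

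**4. Missing post-tests.** The plan expects 75% completion.

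- Loss unrelated to age and arm: main effects moved the mean estimate by at most 0.004, and single data sets by up to 0.12.
- Loss depending on age in opposite directions by arm (a strong assumption; 32 scenarios, 0.5-year gap): main effects moved the mean by 0.02 to 0.28. The bias left was 0.06 to 0.32 when loss widened the age gap and −0.05 to 0.09 when it narrowed it. With × time terms the mean was −0.56 to −0.63.

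**5. Size of the bias.** SE = SD × √(2/232) = 0.2135 (SD 2.3) or 0.3675 (SD 3.96). Error = P(|Z + bias/SE| > 1.96). Power, if the bias works against the effect, = Φ((0.6 − bias)/SE − 1.96).

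| Bias | Share of 0.6 | Error, SD 2.3 | Error, SD 3.96 | Power, SD 2.3 | Power, SD 3.96 |
|---|---|---|---|---|---|
| 0 | 0% | 5% | 5% | 80% | 37% |
| 0.5 × 0.1 = 0.05 | 8% | 5.6% | 5.2% | 73% | 32% |
| 0.5 × 0.3 = 0.15 | 25% | 10.8% | 6.9% | 56% | 23% |
| 1 × 0.3 = 0.30 | 50% | 29% | 12.9% | 29% | 13% |

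The error doubles to 10% at a bias of 0.14 (SD 2.3) or 0.24 (SD 3.96). For sex, a gap of 10 to 20 percentage points and an assumed difference in change of 0.5 to 1 give 0.10 × 0.5 = 0.05 to 0.20 × 1 = 0.20.

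**6. How large a gap chance would give.** Under individual randomisation, with an age SD of 1.7, the SE of the age gap is 1.7 × √(2/300) = 0.139 years. At a slope of 0.3 that is 0.04 in the estimate. A 0.5-year gap is 0.5/0.139 = 3.6 such SEs, so it needs a real shift in intake.

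**7. House and year.** The same algebra applies to a random site intercept: it absorbs level, not change. With houses in opposite arms, stable house differences largely cancel. A year shift in change cancels if intakes are equal. Otherwise the fraction (a − b)/(a + b) remains: 8/72 = 1/9 for houses of 40 and 32, and 24/72 = 1/3 for 48 and 24. In simulation, a year shift of 1 gave −0.599 (36/36), −0.708 (40/32) and −0.933 (48/24) as written. With house × time and year × time the results were −0.599, −0.596 and −0.600. If both houses are in the same arm each year, year and HIHE coincide and no term separates them.

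**The case against.** The strongest reply is that the fault is read into silence. The section never says main effects, and it calls the intervention × time interaction itself a fixed effect, so its wording does not exclude age × time. That is true. But the plan spells out the one interaction it wants and lists covariates without any, so an analyst following it would fit main effects. If × time terms were meant, one sentence settles it.

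Second, no bias is demonstrated. The age gap and the slope are both assumed, and the bias is zero if either is zero. Both houses contribute to both arms over the two years, and a chance-sized gap is worth about 0.04. This stands, and it is why the sizes above are illustrative only. It does not rescue an adjustment that, with complete pairs, cannot alter the estimate.

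Third, the dropout scenarios are severe, and in some of them main effects help. In one, the estimate moves from −0.785 to −0.617 against a truth of −0.6. In the mirror-image scenario it moves only from −0.158 to −0.303. The help depends on the direction of dropout and cannot be relied on.

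Fourth, extra terms cost precision in a trial with little to spare. With 600 × 0.75 = 450 completers, 225 per arm gives about 79% power at SD 2.3. A 4.4% larger SE gives about 76%, and 9.7% about 71%. That cost is real, but its upper end belongs to house and year terms with very unequal houses, not to age and sex.

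**Conclusion.** The concern holds. On the ordinary reading, the planned age and sex adjustment leaves the HIHE estimate exactly as it was with complete pairs, and unchanged on average when post-tests are missing independently of age and arm. This follows from the model and needs no assumption about the data.

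The size of any bias cannot be derived from the documents. Over the assumed age gaps and slopes it is 0.05 to 0.30, or 8% to 50% of the planned 0.6. The larger values need a real change in intake between house-years, which the documents neither show nor exclude. The point should be fixed because allocation by house and year leaves age and sex balance unprotected and the correction is cheap. Confidence is medium, because the wording does not strictly rule out time interactions.

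**What to change.** In *Statistic and power calculation*, state that the model contains age × time and sex × time, and that intervention × time from that model is the reported HIHE effect.

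Reconcile the 1:1 randomisation in that section with the allocation by house and year in *Design* and *Recruitment of participants*. Reconcile those two sections on whether the houses are in opposite arms each year. Then:

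- **Opposite arms:** also specify house × time, with house as a fixed effect, and calendar year × time.
- **Same arm each year:** omit year × time and say in the conclusions that year and HIHE cannot be separated.

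State also what these terms do not do. Four house-year cells are fully used by intercept, house, year and treatment, so residual house-year variation remains unaddressed.

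The change is to wording only. Age and sex are already named covariates, house is the site, and year follows from the date of the test at the start of the stay. In simulation (24 scenarios, both SDs), age × time and sex × time changed the SE of the HIHE effect by −1.1% to +3.7%. Adding house × time and year × time gave −0.8% to +4.4% for houses of 36/36 or 40/32, and +5.2% to +9.7% for the extreme 48/24.

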### Tests and measurements

The participants will be tested in the start and end of their 10-week residential stay at the DCSH.

Furthermore, there are follow-up tests 3 and 12 months after their stay. The, in total, four tests days include measurements of physical fitness, physical performance, cognitive functions and questionnaires about health-knowledge, well-being and sleep patterns. For further descriptions, see below. Each test day is of approx. 4-5 hours duration.

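### As ordinarily read, the programme-by-time test of HIHE compares raw changes and does not adjust for the child's own start-of-stay value; the test is valid but gives up precision, by about 2–4% of variance for fat percentage under the sizing SD

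*Combined protocol and SAP*

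**What the plan says.** The section on statistics and power names fat percentage as primary ("The primary outcome of the project is fat percentage") and puts every outcome through one linear mixed model, "including two-way interaction between intervention (standard and intervention) and time (before and after) as fixed effect". Child and site are random effects. Age and sex are fixed effects, with other covariates left open. The two times come from the section on tests and measurements: "The participants will be tested in the start and end of their 10-week residential stay at the DCSH".

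The plan does not name the start-of-stay value as a covariate, does not say that the two programmes share one start-of-stay mean, and does not say whether a programme main effect is fitted.

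Sizing is by an unadjusted comparison: "The power calculation is measured with t-test" and "The calculations are based on a power of 0.80 and p-value of 0.05". For fat percentage over the stay, the table gives a difference of −0.6 with SD 2.3 and 232 children per group. About 600 children are planned at 75% completion.

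**The concern.** A programme-by-time interaction normally comes with a programme main effect, so each programme gets its own mean at the start of the stay. The interaction then measures how much more one group changed than the other. A child who starts high by chance tends to drift back, and a change score counts that drift as change. Regression on the start value removes it.

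At stake is precision that costs nothing to collect, plus some sensitivity of the estimate to chance differences at the start. The margin on the primary outcome is thin: 75% of 600 is 450 completers, below the 464 in the plan's own table. The same model serves the questionnaires, health knowledge and the cognitive tests, where r may be lower (an assumption).

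**Working it through.** **Inputs from the plan.** Difference 0.6 and SD 2.3 (read as percentage points of body fat, and as the SD of change); arm SDs 4.2 and 3.7; power 0.80; p-value 0.05 (taken as two-sided); 1:1 allocation; 600 × 0.75 / 2 = 225 completers per arm.

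**Assumed, because the plan does not give them.** Baseline SD s of fat percentage 6–8 points; equal SD before and after; children treated as independent.

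**1. The plan's own figure.** 2 × (2.3/0.6)² × (1.96 + 0.84)² gives 231 per group by the normal approximation. The t-test gives 232, as stated.

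**2. What the interaction estimates.** Child and site intercepts, age, sex and the programme main effect are constant within a child, so they cancel from after minus before. With complete pairs, only the difference in mean change is left. One simulated data set (225 per arm, r = 0.8, child intercept, age and sex) confirms it:

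| Analysis | Estimate | SE |
|---|---|---|
| Mixed model, programme × time | −0.3766 | 0.2238 |
| Two-group comparison of change | −0.3766 | 0.2238 |
| End value regressed on start value, age, sex | −0.3989 | 0.2113 |
| Mixed model, one common start mean | −0.3993 | 0.2127 |

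The last two have about 10% less variance, since (0.2113/0.2238)² = 0.89 and (0.2127/0.2238)² = 0.90. With about 25% of the end values missing, the mixed model gave −0.430 (SE 0.260) and the completers' change scores −0.360 (SE 0.264). The identity is then no longer exact, but the comparison is still not adjusted for baseline.

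**3. Variance ratio.** The variance of a change is 2(1−r)s². After adjustment it is (1−r²)s². The ratio is (1+r)/2.

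**4. Primary outcome, SD of change 2.3.** From 2.3² = 2(1−r)s², 1−r = 5.29/(2s²).
- s = 6: 1−r = 0.073, r = 0.93, saving (1−r)/2 = 3.7%.
- s = 8: 1−r = 0.041, r = 0.96, saving 2.1%.

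The SE at 225 per arm is 2.3 × √(2/225) = 0.217, so change-score power is Φ(0.6/0.217 − 1.96) = 79.0%. Multiplying the SE by √0.963 or √0.979 gives 80.5% or 79.8%.

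A one-standard-error start difference is s√(2/225) = 0.566 (s = 6) or 0.754 (s = 8). Multiplied by 1−r, the shift is 0.042 or 0.031, which is 7% or 5% of 0.6.

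**5. Primary outcome, arm SDs as the SD of change.** The pooled SD is √((4.2² + 3.7²)/2) = 3.96, and 3.96² = 15.7.
- s = 6: 1−r = 15.7/72 = 0.218, r = 0.78, saving 10.9%, shift 0.218 × 0.566 = 0.12.
- s = 8: 1−r = 15.7/128 = 0.122, r = 0.88, saving 6.1%, shift 0.122 × 0.754 = 0.09.

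The SE is now 3.96 × √(2/225) = 0.373. Power is Φ(0.6/0.373 − 1.96) = 36% for the change score and about 38–40% with adjustment.

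**6. Other outcomes.** The saving (1−r)/2 is 25% at r = 0.5, 15% at 0.7 and 5% at 0.9. The plan gives no r for any outcome.

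**The case against.** **The planned test is sound on average.** If both programmes draw on the same pool of children, the change-score test is unbiased and its SE already carries the noise from chance imbalance. This stands. A reader might infer that the analysis is invalid; the plan does not support that.

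**A large gain for the primary outcome is tempting but unsupported.** At r = 0.5, power at 225 per arm would go from 79% to 89%. With an SD of change of 2.3, however, r = 0.5 implies a baseline SD of 2.3/√(2 × 0.5) = 2.3 points, far below the assumed 6–8. A reader might also infer that a one-standard-error imbalance moves the estimate by 10–25% of the target, from a baseline SD of 6–8 with r of 0.8–0.9. Those values imply an SD of change between 6 × √0.2 = 2.7 and 8 × √0.4 = 5.1, so they cannot be combined with power figures built on 2.3.

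**The gain may fall where it is least needed.** For health knowledge the table asks for 100 per group and about 225 are expected; with its 9.4 and SD 23.5, power is already about 99%. This stands for the outcomes in the table, but not for the cognitive tests and the other questionnaires, which are not sized.

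**Children are not individually randomised.** The table says "The calculations are based upon a randomisation of 1:1, 50% of the participants participate in the standard program", but the design section describes a cross-over of two houses over two years. The recruitment section can even be read as both houses running HIHE in the same year. Start-of-stay differences may then be systematic. If the groups would have changed in parallel, it is the adjusted analysis that is off, by about (1−r)D. This limits the claim but does not defeat it. On the cross-over reading both houses supply both programmes. The same factor bounds the disagreement: per point of D it is 0.04–0.07 under the sizing SD.

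**The plan is silent on the programme main effect.** If it is left out, the start means are common and the model already adjusts for baseline. That is possible, and it is a reason to say so.

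**Conclusion.** The point holds as one of efficiency and clarity, not validity. On the ordinary reading, the HIHE estimate with complete pairs is the raw difference in mean change, and the start-of-stay value is not used to adjust it.

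For fat percentage under the plan's sizing SD, the loss is small: 2–4% of variance, about one percentage point of power, and a shift of 0.03–0.04 per one-standard-error imbalance. If the arm SDs describe the true spread of change, the saving is about 6–11%, but power is well below 80% under either analysis and baseline adjustment does not rescue it. Outcomes with lower r gain more.

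All these sizes rest on the assumed baseline SD or r, on equal SDs before and after, and on independent children. The change is worth making because it is nearly free and because the two analyses can give different answers, so the choice should be fixed in advance.

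**What to change.** In the statistics section, state that the HIHE comparison models the end-of-stay value on programme, with the child's start-of-stay value of the same outcome, age and sex as covariates and the site term retained. The near-equivalent is a mixed model on both times with one common start-of-stay mean for the two programmes. Keep the planned interaction, with its programme main effect stated, as a sensitivity analysis, and report any disagreement between the two.

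The cost is one or two sentences and no new data, visits or children. The downside is the assumption that both programmes draw on the same pool of children. Because programmes switch by house and year, neither analysis removes house-by-period confounding, and the text should say so.

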## Aim

The aim of the project is to document the short-term effects on health, physical fitness, physical activity level, learning, sleep and well-being from a 10 weeks residential stay on one of the Danish Christmas Seal Houses. Furthermore, to document the long-term effects 3 and 12 months after the stay. In addition, the project examines if a special effort with a high intensity activity/health education program (HIHE) increases the effects on physical fitness and health knowledge, learning capabilities, sleep patterns, well-being and adherence to a physical active lifestyle compared to the standard program.

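### The single stated model has only two time levels, so it gives no separate programme effect at 3 or 12 months, although both visits are in the aim and a follow-up contrast is sized

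*Combined protocol and SAP*

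**What the plan says.** The section Statistic and power calculation gives one model and applies it throughout: "All outcomes will be analyzed by means of linear mixed models". Its fixed part is a "two-way interaction between intervention (standard and intervention) and time (before and after) as fixed effect", and its random part is "child and site as random effects". No residual covariance structure is given, and the two levels in "time (before and after" are not defined further.

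The design has more occasions than that. Under Tests and measurements, "The participants will be tested in the start and end of their 10-week residential stay at the DCSH", and "there are follow-up tests 3 and 12 months after their stay", four test days in all. The Aim section includes the wish "to document the long-term effects 3 and 12 months after the stay". The Hypothesis section expects better adherence to an active lifestyle with HIHE, and the section on publication promises both short- and long-term results.

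The power table has two rows for fat percentage, the primary outcome. The row for the intervention period has mean changes of -9.6 (SD 4.2) and -8.9 (SD 3.7), a difference of -0.6 (SD 2.3) and 232 per group. The row for the follow-up period has 5.0 (SD 13.4) and 8.4 (SD 12.9), a difference of -3.3 (SD 11.2) and 182 per group. The table does not say whether follow-up means 3 or 12 months, from which visit the change is counted, or whether the units are percentage points or relative percent.

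**The concern.** A two-level time factor can hold two occasions. With four, the analyst must decide what before and after mean for the later visits, and the plan does not decide it. Before could be baseline or end of stay, and after could be 3 or 12 months. That leaves four candidate long-term contrasts for a primary outcome that has no named time point.

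Two things are at stake. First, the long-term results, both for the stay itself and for HIHE against standard, have no pre-specified estimate, so the contrast could be chosen after the data are seen. Second, simply adding the two later visits to the stated model can misstate the standard errors, because a child random intercept with one residual variance treats the change between any two visits as equally variable. The plan's own SDs say otherwise.

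**Working it through.** **1. The plan's sample sizes.** For a two-sided comparison of two mean changes, alpha 0.05 and power 0.80, n per group = 2 × (1.960 + 0.842)² × (SD/difference)².

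- Intervention period: 15.70 × (2.3/0.6)² = 15.70 × 14.69, giving 231; the t-test version gives 232, as stated.
- Follow-up period: 15.70 × (11.2/3.3)² = 15.70 × 11.52, giving 181; the t-test version gives 182, as stated.

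Each row is a stand-alone two-point change with its own effect and SD. The in-stay row is the larger (464 in total, 580 after the plan's allowance for losses) and so sets the target of about 600.

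**2. What pooling would estimate.** Suppose all three later visits are coded as after, with equal retention, and the follow-up row applies at both 3 and 12 months.

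- Follow-up row read as change from end of stay: the differences from baseline are -0.6, -3.9 and -3.9. Mean = -8.4/3 = -2.8.
- Follow-up row read as change from baseline: -0.6, -3.3 and -3.3. Mean = -7.2/3 = -2.4.

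Subtracting the printed arm means gives -9.6 + 8.9 = -0.7 and 5.0 - 8.4 = -3.4 instead of -0.6 and -3.3. The pooled values are then (-0.7 - 4.1 - 4.1)/3 = -3.0 and (-0.7 - 3.4 - 3.4)/3 = -2.5. On each reading the pooled figure is about four times the end-of-stay effect and smaller than the follow-up effect. The first reading adds changes, which is valid only if the units are percentage points.

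**3. SDs of change.** Pooling the two arms:

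- Stay: √[(4.2² + 3.7²)/2] = √15.67 = 3.96.
- Follow-up: √[(13.4² + 12.9²)/2] = √172.99 = 13.15.
- SD ratio 13.15/3.96 = 3.3; variance ratio 172.99/15.67 = 11.

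**4. Effect on the standard errors.** Take four visits, complete data, a child random intercept and one residual variance. The model then gives every between-visit change the same variance, namely the average of the six pairwise change variances. Assume the stay change and the follow-up changes are independent, and let r be the correlation between the two follow-up changes. The six variances are:

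- baseline to end of stay: 15.67
- two changes that combine stay and follow-up: 15.67 + 172.99 = 188.65 each (from unrounded inputs)
- two follow-up changes: 172.99 each
- 3 to 12 months: 2 × 172.99 × (1 - r)

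The set is the same whether the follow-up row is counted from end of stay or from baseline.

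- r = 0: (15.67 + 377.30 + 345.97 + 345.97)/6 = 180.8. Standard error ratio for end of stay: √(180.8/15.67) = 3.4.
- r = 0.9: (15.67 + 377.30 + 345.97 + 34.60)/6 = 128.9. Ratio: √(128.9/15.67) = 2.9.

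The standard error of the end-of-stay contrast is therefore overstated about 2.9 to 3.4 times. For a follow-up contrast with true variance 188.65, the ratio is √(128.9/188.65) = 0.83 to √(180.8/188.65) = 0.98, so it is somewhat understated.

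With only two visits the same structure is harmless: there is one change, and the residual variance is half its variance. The problem appears when visits are added without changing the covariance.

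**The case against.** The strongest reply is that nobody proposed to drop or pool the follow-up tests. The stated model can be fitted once per interval: start to end of stay, start to 3 months, start to 12 months, or end of stay to follow-up. The separately sized follow-up row points that way. Such models would each have their own residual variance, which removes the standard-error problem. This stands, and it is why separate models are an acceptable remedy. It does not close the gap, because the plan does not say so and does not name the intervals.

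A reader might infer that the later visits must be either left out or merged with end of stay, and that the long-term aim therefore cannot be answered. The documents do not support that. Separate interval models are a third route, all four test days are scheduled, and the model extends directly.

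It is also fair that the pooled figures describe an analysis the plan does not propose, and that they depend on an unstated reference visit, follow-up visit and unit. They illustrate the cost of one possible coding and are not predictions. Nor should the raw -3.3 be read as a much larger benefit: standardised by the table's own SDs the two effects are close (0.6/2.3 = 0.26 and 3.3/11.2 = 0.29).

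Finally, the SDs come from earlier studies, and a larger SD of change may reflect weaker within-child correlation rather than larger variance at the later visits. Either cause conflicts with a model that gives all changes one variance, so the warning stands, but its size in this trial is not known.

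**Conclusion.** The point holds as a gap between the stated model and the design. Followed literally, the model yields no distinct 3- or 12-month effect, while the plan aims at both time points and sizes a follow-up contrast. The text supports that without any numerical assumption.

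The sizes are conditional. A pooled after level would give roughly -2.4 to -3.0, against -0.6 to -0.7 at end of stay, if the follow-up row applies equally at both later visits and retention is equal. The overstatement of 2.9 to 3.4 times applies only if four visits are put into one model with a child random intercept and a single residual variance. It also assumes complete data, the table's arm-level SDs, and independent stay and follow-up changes. Adding time levels alone is therefore not a sufficient repair.

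This should be corrected before analysis. It does not undermine the trial, because the scheduled visits can support the long-term estimates once the analysis is specified.

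**What to change.** Amend Statistic and power calculation as follows.

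- **Time:** a four-level categorical factor (baseline, end of stay, 3 months, 12 months) with the programme-by-time interaction.
- **Contrasts:** name one for each aim. For HIHE against standard, the programme difference in change from baseline to end of stay is primary, because that row sets the sample size. The differences at 3 and 12 months from baseline are secondary, with 12 months minus end of stay if maintenance is of interest. For the effect of the stay itself, name the corresponding within-programme changes.
- **Covariance:** allow visit-specific variances and correlations within child, for example an unstructured matrix in place of the child random intercept. Alternatively, state that a separate two-visit model is fitted for each named interval.
- **Power table:** say whether the follow-up row refers to 3 or 12 months, from which visit the change is counted, and in which units.

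The cost is plan wording. An unstructured matrix for four visits has 4 variances and 6 covariances, 10 parameters against 2 for a random intercept with one residual variance. That is small beside the roughly 450 children expected at 75% completion of 600, although the plan gives no completion rate specific to 3 or 12 months. No new visit or participant is needed, since all four test days are already planned.
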